#### **7.3.1.2. When is it measured?**

The secondary outcome measure of health status (EQ-5D-5L) will be measured at three time points: baseline, 3-month and 6-months post baseline.

#### **7.3.1.3. For whom is it measured?**

EQ-5D-5L will be collected for all service users across intervention and control sites.

#### **7.3.1.4. Measure and validation**

The EQ-5D-5L is a health-related quality of life (HRQL) instrument that has been validated in various contexts. The descriptive system of EQ-5D-5L comprises five dimensions: mobility, self-care, usual activities, pain/discomfort and anxiety/depression. Each dimension has five levels: no problems, slight problems, moderate problems, severe problems and extreme problems (Appendix D). The patient is asked to indicate their health state by ticking the box next to the most appropriate statement in each of the five dimensions. This decision results in a 1-digit number that expresses the level selected for that dimension. The digits for the five dimensions can be combined into a 5-digit number that describes the patient's health state. Health state index scores generally range from less than 0 (value of a health state equivalent to dead; negative values representing values as worse than dead) to 1 (the value of full health), with higher scores indicating higher health utility.

The EQ VAS records the patient's self-rated health on a vertical visual analogue scale where the endpoints are labelled 0 = 'The worst health you can imagine' and 100 = 'The best health you can imagine' (Appendix D). The VAS can be used as a quantitative measure of health outcome that reflects the patient's own judgement.

### **7.3.2. Interactions with health services**

#### **7.3.2.1. Instrument**

Basic data on health service interactions/health service resource use will be captured using questions adapted from the MHCLG Rough Sleeping Questionnaire (RSQ) (Appendix E).

#### **7.3.2.2. When is it measured?**

The health service resource use questions will be asked at the baseline, 3-month and 6-months follow-up time points.

#### **7.3.2.3. For whom is it measured?**

Health service resource use will be collected for all service users across intervention and control sites.

#### **7.3.2.4. Measure and validation**

This is not a validated measure. The service interaction types are routinely captured by MHCLG in the RSQ.

## **8. DATA COLLECTION**

### **8.1. Data Collection Methods**

In intervention sites, housing situation data (primary outcome), health status data (secondary outcome), and health service interaction data (secondary outcome) will primarily be collected by nurses as part of their normal routine service delivery at baseline, 3 and 6 months. They will also be supported by a dedicated CGL team member and outreach workers. At follow-up, service users will either be recontacted on the streets, contacted using known telephone numbers, or nurses/CGL team member will seek to locate individuals through other service providers (e.g. hostels and day centres). CGL will amend their routine data collection platform to capture outcome data.

In control sites, housing situation data (primary outcome), health status data (secondary outcome), and health service interaction data (secondary outcome) will be collected by outreach workers as part of their normal routine service delivery at baseline. At follow-up, a dedicated CGL team member will support the collection of follow-up data at 3 and 6 months in control sites. Service users will either be recontacted on the streets, using known telephone numbers, or the CGL team member will seek to locate individuals through other service providers (e.g. hostels and day centres). The CGL team member will work across all control sites, potentially travelling between them to aid sites in collating data. They will also assist the local teams in their data uploading and in tracking service users who have previously been included as part of the study and following-up with these service users.

Data will be manually input into the CGL managed CRi Information System (CRiIS). For intervention sites, baseline data will be entered by the outreach nurse, and follow-up data with assistance from a CGL team member. For control sites, the relevant data extracts will be provided to CGL, then all data will be manually entered into CRiIS by the CGL team member.

As data will be collected by nurses and/or outreach workers ('users') as part of their everyday service delivery, there will be an element of user preference determining how it is collected. Staff can either enter data directly into the database using a CGL provided mobile device whilst they are with the service user or make paper notes and transfer them at the office via the online portal.

To aid in managing the burden on staff in collecting additional routine data, sites will be informed that they can stop collecting data once they have reached a caseload of 120. A larger sample size would have very limited benefit to the study, whereas the withdrawal of a Local Authority due to data collection challenges would have a significant impact.

**Table 9: Data Collection Procedures and Assessment Timeline**

Assessment point	Type of data	Data collection approach
First contact (four-week window to collect baseline)	Contact recording and eligibility assessment.	Nurses and outreach workers. On the street/in the community.
Baseline	Baseline characteristics (age, sex, gender, nationality, care experienced, left an institution in the last 85 days – see Appendix F), primary and secondary outcomes (pre-intervention).	Nurses and outreach workers. On the street/in the community.
Interim contact data*	Contact date for each contact occurrence with service user to record data and/or to receive treatment, care or advice.	Nurses and outreach workers and CGL team member. On the street/in the community (intervention sites only).
Midline (3 months after baseline – 4-week window to complete)	Primary and secondary outcomes including reason for non-contact if applicable.	Nurses, outreach workers, and CGL team member. On the street/in the community, telephone (if contact details provided), through other organisations (e.g. NHS).
Interim contact data*	Contact date for each contact occurrence with service user to record data and/or to receive treatment, care or advice.	Nurses and outreach workers and CGL team member. On the street/in the community (intervention sites only).
Endline (6 months after baseline – 4-week window to complete)	Primary and secondary outcomes including reason for non-contact if applicable	Nurses, outreach workers, and CGL team member. On the street/in the community, telephone (if contact details provided), through other organisations (e.g. NHS).

\*Interim contact data collected in intervention sites only to assess level of contact per service user, treatment, care or advice given (anonymised), and to facilitate follow-up data tracking

## 8.2. Retention Strategies

Individual service user routine data collection engagement and retention will be managed by nurses and outreach workers and a CGL team member. Service user interview engagement and participation will be managed by nurses and outreach workers and an evaluation team member.

When appropriate, and as a token of gratitude for their time, service users may be provided with 'thank you' vouchers. This is perceived to be fair compensation for an individual's time.

For routine data collection, this will be in the form of a food and drink voucher up to the value of £10, so the individual can purchase something to eat or light refreshment (e.g. a coffee). In the intervention areas, the nurses also have payment cards with which they could buy food or coffee for individuals to increase engagement. This is a common tool for many front-line homelessness services and would not be out of usual practice for the outreach team or service users in control areas, enabling equality across the two groups and encouraging engagement for the important follow-up at 3 and 6 months.

As a thank you for participating in an individual interview, service users in intervention and control sites will be offered a £20 high street shopping voucher. CHI Lived Experience Network members input into developing this strategy.

## 8.3. Data Management Procedures

Pseudo-anonymised datasets from the CRIS database will be extracted as csv files and securely transferred electronically from CGL to Cardiff University using an access-managed Microsoft Teams space. Data downloads will be monthly, to allow checking for data completeness. At Cardiff University, the data will be stored on a secure server, only accessible to staff who have been given access. Access is controlled by the Trial Manager and is a delegated duty outlined on the trial delegation log.

Trial data provided by CGL will be de-identified before transfer. Any potentially identifiable data such as date of birth or open text fields will be checked and recoded by CGL (i.e. DOB calculated as age at time of data collection, treatment care or advice given – names and locations redacted and study ID number removed).

Due to the nature of the data collection, Cardiff University Data Managers will be unable to validate source data. All data will be collected and handled by CGL acting on behalf of the data controller, MHCLG as per their data protection policy, which can be found here: <https://www.gov.uk/government/organisations/ministry-of-housing-communities-local-government/about/personal-information-charter>.

Qualitative data (service user and staff interviews/observational data) will be transferred directly to Cardiff University servers following data collection. Interview audio recordings will be labelled with participant identification numbers. All transcripts will be checked for accuracy

and identifiable information will be removed or anonymised (e.g. removing names/location/gender).

The full Cardiff University data management procedures for Test & Learn: Outreach services with a health specialism for people rough sleeping may be seen in the project data management plan which will cover Cardiff University data management processes. This is available on request.

## 9. SAMPLE SIZE AND POWER CALCULATION

### 9.1. Sample Size / Power Calculation

The aim of this pilot cRCT is to evaluate feasibility and acceptability of outreach services with a health specialism for people rough sleeping and provide indicative evidence of its effectiveness. The study will determine numbers of service users eligible for routine data collection and response rates, estimates of effect sizes and intra-cluster correlation coefficients as well as providing in-depth knowledge on the views and experiences of health outreach workers and people who received care.

A sample size calculation was provided by CHI based on the number of LAs and service users that could viably be engaged within the time and budget available. The sample size was based on 80% power, 5% alpha, a minimum detectable effect size (MDES) of 0.53, an average cluster size (LA) of 40 service users, ICC of 0.1, allocation ratio 1:1, and 10% attrition (Table 10). We therefore aim to randomise 16 clusters (LAs) with 8 to receive funding to embed a health professional as part of the outreach team (a qualified nurse) and 8 to remain with their usual practice, with a total of 711 LA service users required in total.

**Table 10: Sample Size Calculations**

		Overall
Minimum Detectable Effect Size (MDES)		0.53
Pre-test/ post-test correlations	level 1 (service user)	-
	level 2 (cluster)	-
Intracluster correlations (ICCs)	level 2 (cluster)	0.10
Alpha		0.05
Power		0.8
Alternative hypothesis: One-sided or two-sided		Two-sided
Average cluster size		40
Number of clusters	Intervention	8
	Control	8
	Total	16

Number of service users	Intervention	320
	Control	320
	Total	640
Expected attrition at cluster level	%	0
Expected attrition at individual level	%	10
Effective sample (Clusters)	Total	16
Effective sample (Service users)	Total	711

## 9.2. Attrition Assumptions

As this is a pilot cRCT, estimating a realistic rate of attrition in service users is an objective of this study.

## 10. ANALYTICAL STRATEGY

A detailed statistical analysis plan will be written and finalised before any analysis is undertaken. A brief overview of the intended approach is detailed below. The reporting of findings will be in accordance with the CONSORT guidelines for randomised pilot and cluster RCTs. All analyses will be performed in Stata v17.0 or R.

### 10.1. Analytic Sample

All analyses will be on an intention to treat (ITT) approach and will include service users that are included in the study, irrespective of how much intervention is received.

### 10.2. Descriptive Statistics

A CONSORT flow diagram will show the number of LAs recruited and randomised, and withdrawals after randomisation of LAs as well as the number of service users included, and completion of baseline interview and follow-up points. The feasibility criteria relating to data collection on the primary outcome at baseline and follow-up will be reported as point estimates with 95% confidence intervals (CIs) (Campbell et al., 2012; Eldridge et al., 2016). We will also describe the number of interim contacts over the 6-month follow-up period intervention sites.

We will tabulate baseline characteristics of both the LAs (e.g. region, RSI funding allocation 2022-2025 strata) and the service user characteristics measured at baseline (e.g. age (years), sex assigned at birth, gender identity, nationality, care experienced, left an institution in the last 85 days – see Appendix F); these will be shown by trial arm and summarised using means and standard deviations (SDs) (or medians and interquartile (IQR) ranges, as appropriate) for continuous outcomes, frequencies and percentages for categorical outcomes.

### 10.3. Analyses

As this is a pilot RCT, point estimates and 95% CIs will be presented but p-values for hypothesis testing will not. It is important that these tests are interpreted in the context that they are not fully powered such that a smaller effect would not suggest the intervention was ineffective. However, if the 95% CIs indicates significant benefit, then another trial would not be necessary.

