#### **2.1.2. Phase 2 - Pilot cluster randomised controlled trial with an integrated implementation and process evaluation, and economic evaluation**

After the programme theory has been confirmed and any intervention modifications have been made, a pilot cRCT with an integrated implementation and process evaluation, and economic evaluation, will be carried out in Phase 2 in 16 Local Authorities (LAs) in England,

randomising 8 areas to receive the nurse outreach intervention and 8 to remain with their usual practice (control).

The objectives of Phase 2 are to:

1. Assess the viability of the intervention, and barriers and facilitators to implementation, including contextual factors, acceptability to LAs, nurses and service users, engagement of service users, and fidelity of intervention delivery.
2. Identify and explore the mechanisms of change through which the intervention works.
3. Determine the feasibility of the trial methods, including LA recruitment and randomisation, LA and service user retention, data collection processes – including the proportion of service users present in routine data collection, as well as any adaptations.
4. Offer suggestive evidence of the impacts of the intervention on the housing situation and health of individuals, as well as intervention costs and benefits.

Pilot cRCT activities will include:

- Recruitment and randomisation of LAs.
- Analysis of routine data in intervention and control sites relating to demographics, health and housing outcomes of people living on the streets.
- Qualitative interviews with key staff and people living on the streets in intervention and control areas, and LA representatives (if any site withdraws from the cRCT).
- Observation of practice.
- Analysis of staff time and resource logbooks.

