the multilevel mixed-effects generalised linear model for our analysis can be described as follows:

$$g(y|X, u) = X\beta + Zu + \varepsilon$$

The fitted model can be formulated as bellow:

$$g\{E(y|X, u)\} = X\beta + Zu$$

where:

- $y \sim F$  (i.e., the outcome  $y$  follows a distribution  $F$  (e.g., normal, binomial, ordinal etc.))
- $y$  is the ( $n \times 1$ ) vector of responses from the distribution  $F$  such as for the outcome level 1, it takes values as (1=stable but secure), (2=stable but insecure), (3=hidden, temporary and/or unstable), (4=rough sleeping).
- $X\beta + Zu = \eta$  is called a linear predictor and its terms are described as below:
- $X$  is an ( $n \times p$ ) design/covariate matrix for the fixed effects  $\beta$  including the study arms (intervention=1 versus control=0) and LAs RSI funding allocation 2022-2025 strata (e.g., 0=low RSI funding allocation, 1=high RSI funding allocation) and other baseline covariates such as service users' age and gender.
- $Z$  is the ( $n \times q$ ) design/covariate matrix for the random effects  $u$  assumed to be normally distributed with mean 0 and ( $q \times q$ ) variance matrix ( $\Sigma$ ). In this study, it may be kept limited to the random effect of local authority (clusters) only matrix  $\Sigma$ .

The effect size will be reported as an absolute risk differences (intervention minus control) alongside 95% CIs, at each time point. Adjusted relative risk ratios for intervention versus control will be computed from the model presented alongside 95% CI. We will also estimate the clustering of outcomes by trial arm via intra-cluster correlation coefficients (with 95% CIs). The effect estimates will be used for the sample size calculation of a future definitive study.

For analysis of the Level 1 outcome, the outcome will be a binary outcome (homeless=0 vs not homeless=1) and a mixed effect logistic regression model, with the assumption of binomial distribution, will be used to compute the point estimate as relative risk ratios alongside 95% CI.

For the categorical (ordinal) outcome of Level 3 all twelve categories (A1 to E12) will be included. The mixed-effects generalised linear model will be fitted with the assumption of ordinal distribution, a logistic link function and a suitable linear predictor  $\eta$  including a random effect of the Local Authority. In all analyses, model assumption will be evaluated to insure a best fit of the model.

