## 10.5. Secondary Analyses

We will describe the rates of completion of the health status outcome reporting the five items from the EQ5D using frequencies and proportions. The total EQ5D score will be reported at each time point (baseline, 3 and 6 months) using means (SD), or median (IQR) as appropriate. The modelling approach for EQ5D total score will follow the same approach using a mixed-effects generalised linear model. The outcome measure, total EQ5D score at 3 and 6 months follow-up, will be assumed to be normally distributed, and a mixed-effects generalised linear model will be fitted with the assumption of normality( $F$ ) $\eta$  including fixed-effects for the baseline EQ5D score, interactions of intervention arms and time points (3 or 6 months follow-up) and LAs RSI funding allocation 2022-2025 strata, and a random effect for the Local Authority. The model fit will be assessed using appropriate statistics including residuals, in case of any departure from the model assumptions, an alternative method of modelling such as Generalised Estimating Equation (GEE) will be explored. A similar approach of analysis will be taken with the EQ VAS score (between 0='The worst health you can imagine' and 100='The best health you can imagine').

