## **10.10. Adjustment of Confidence Intervals and p-values for Multiple Statistical Tests**

As a pilot, our analyses are exploratory rather than confirmatory; no statistical testing will be performed, and no p-values will be reported. Therefore, no adjustment for multiplicity will be undertaken.

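### Section 10.3 lets a favourable 95% CI from this pilot make a further trial unnecessary, which contradicts the exploratory, no-testing status that the protocol declares elsewhere

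*Protocol*

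**What the plan says.** Section 10.3 says that point estimates and 95% CIs will be presented without p-values. It warns that the comparisons should be read knowing that "they are not fully powered such that a smaller effect would not suggest the intervention was ineffective". It then adds that "if the 95% CIs indicates significant benefit, then another trial would not be necessary". No outcome, housing level or time point is named.

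Other sections describe a different kind of study:

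- Section 10.10: "As a pilot, our analyses are exploratory rather than confirmatory; no statistical testing will be performed, and no p-values will be reported". The next sentence draws the consequence: "Therefore, no adjustment for multiplicity will be undertaken".
- Section 2.1.2, fourth objective of Phase 2: "Offer suggestive evidence of the impacts of the intervention on the housing situation and health of individuals".
- Section 10.4: "The effect estimates will be used for the sample size calculation of a future definitive study".
- Section 7.1 makes the feasibility criteria in Table 8 the main outcome of the pilot.

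Section 10.4 names one primary analysis, Level 2 housing situation at 6 months. Sections 10.4 and 10.5 together also produce intervals for housing Levels 1 and 3, the EQ-5D score and the EQ VAS, with 3-month as well as 6-month results.

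**The concern.** Checking whether a 95% CI excludes no effect in the favourable direction is a test at one-sided 2.5%, whether or not a p-value is printed. Acting on the result by declaring further trials unnecessary makes that test confirmatory. Section 10.10 justifies having no multiplicity control by the absence of testing, so the justification fails once the rule in 10.3 operates.

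The trigger is also undefined. A reader of the final report could apply the sentence to whichever interval happened to exclude zero. At stake is whether the research question is closed on a false positive or an inflated estimate, from a study that the protocol itself calls underpowered and exploratory.

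**Working it through.** **1. Reproduce the design figure.** Inputs from section 9.1 and Table 10: 8 clusters per arm, 40 service users per cluster, ICC 0.10, two-sided alpha 0.05, power 0.80, MDES 0.53.

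- Design effect = 1 + (40 − 1) × 0.10 = 4.9.
- SE of the standardised difference = √(2 × 4.9 / 320) = 0.175.
- MDES with normal quantiles = (1.960 + 0.842) × 0.175 = 0.490.
- MDES with t on 14 df = (2.145 + 0.868) × 0.175 = 0.527; on 13 df, (2.160 + 0.870) × 0.175 = 0.530.

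The stated 0.53 reproduces with t degrees of freedom and not with normal quantiles.

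**2. Error rate if the trigger is left open.** Assume that each of three housing levels is modelled at 3 and 6 months (6 intervals), plus EQ-5D at both times (2) and EQ VAS at both times (2), which makes 10. Assume no true effect and exact 95% coverage. One interval shows false benefit with probability 2.5%. If the ten were independent, the chance of at least one would be 1 − 0.975¹⁰ = 22.4%. Simulation with correlated normal statistics gives:

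| Correlation among the ten intervals | At least one false benefit |
|---|---|
| 0 (independent) | 22.4% |
| 0.3, all pairs | 17.8% |
| 0.5, all pairs | 14.3% |
| 0.8, all pairs | 8.6% |
| Block pattern: housing levels 0.8–0.9, across time 0.5–0.6, EQ-5D with VAS 0.5–0.6, housing with health 0.1–0.2 | about 13–16% |

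Six of the ten intervals come from recodings of one questionnaire item (Appendix C), so independence is not credible. A range of roughly 9–16% is reasonable.

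**3. What a qualifying result looks like.** At the planned SE, the smallest estimate whose interval excludes zero is 2.145 × 0.175 = 0.375 (14 df) or 2.160 × 0.175 = 0.378 (13 df), so about 0.38 SD. As an illustration, assume a true effect of 0.30 SD and hold the SE at 0.175. The cut-off lies (0.375 − 0.30) / 0.175 = 0.43 SE above the truth. The mean of the qualifying estimates is 0.30 + 0.175 × φ(0.43) / [1 − Φ(0.43)] = 0.30 + 0.175 × 1.09 = 0.49, about 1.6 times the truth.

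**4. Coverage with 16 clusters.** In 100,000 simulated null trials (16 clusters of 40, ICC 0.10, adjusted for stratum, Gaussian outcome), the two-sided error of a nominal 95% interval was 9.8% for maximum likelihood with normal limits, 7.0% for REML with normal limits, and 4.9% for REML with t on 13 df. Coverage is therefore about 90%, 93% and 95%. Binary and ordinal models will differ somewhat.

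**The case against.** The strongest reply is that the sentence is a remark on interpretation, not a formal rule. On that view section 10.4 names a single primary contrast, section 7.2.3 makes 6 months the primary time point, and Table 8 remains the main outcome under the Trial Steering Committee. Part of this stands: nothing in 10.3 switches off the feasibility criteria. But the sentence states a consequence for future research, does not refer to the primary contrast or to Table 8, and cannot be squared with 10.10 as written.

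Some stronger readings are tempting, and the protocol does not support them:

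- A reader might infer that the planned intervals under-cover. The protocol gives the model and the random effect but not the CI method, which may properly be left to the SAP. The MDES reproduces only with t degrees of freedom, which suggests that small-sample thinking was present at design. The GEE alternative in section 10.5 ("an alternative method of modelling such as Generalised Estimating Equation (GEE) will be explored") is only a contingency for the health scores, with no SE type stated. Under-coverage is a conditional risk.
- A reader might infer that the text says any interval suffices. It does not; it merely fails to say which one counts. The count of ten is an assumption, because section 10.4 promises only the risk difference at each time point.
- A reader might fault the caution that a small effect would not show ineffectiveness. For an underpowered pilot that caution is correct.
- Sizing the next trial from the pilot's effect estimate is a separate matter. Section 10.4 is relevant here only because it presupposes a definitive study.

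**Conclusion.** The contradiction is real and should be removed before any results are interpreted. It does not depend on the simulations: at exact 95% coverage and for a single interval, 10.3 still performs a test that 10.10 says will not be performed.

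The size of the problem depends on how the sentence is applied. Confined to one pre-named contrast with a valid interval, the false-benefit rate is 2.5%. Left open across about ten intervals, it is roughly 9–16% for plausible correlations. In both cases a qualifying estimate would tend to exaggerate the effect, given the stated ICC, cluster size and number of clusters. Possible under-coverage would add to this only if normal-based limits were used.

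**What to change.** Delete the sentence in section 10.3. In its place, state that no confidence interval from this pilot will be used to conclude that a definitive trial is unnecessary, and that progression rests on the Table 8 criteria.

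If the sponsor wishes to keep a rule of this kind, limit it to the pre-named primary contrast (Level 2 housing situation at 6 months), specify a small-sample, t-based interval for it, and rewrite sections 10.10 and 10.4 so that they no longer describe the analyses as free of testing or take a definitive study for granted.

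The preferred change costs wording only: no data, no sample size and no planned estimate is affected. The pilot gives up the option of declaring the question closed, which its stated aims do not claim.
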